4.2 Inclusion and Exclusion Criteria

4.2.1 Inclusion Criteria

To be eligible for inclusion, a patient must comply with all of the following criteria:

- First prescription of Cystistat according to instructions for use.
- Female patients of any ethnic origin with clinical diagnosis of interstitial cystitis (IC)/bladder pain syndrome (BPS). If in accordance with routine clinical practice at the site, ESSIC diagnostic criteria will be used.
- Age: 18 years and older.
- At least 6 months duration of bladder pain/discomfort symptom(s), e.g. constant bladder pain/discomfort or bladder pain/discomfort when voiding or as a burning sensation between voids as the bladder fills with urine.
- At least one accompanying intermittent or persistent lower urinary tract symptom, such as urinary frequency, urgency, or nocturia during the previous 6 months.
- Bladder Pain/ Interstitial Cystitis Symptom Score (BPIC-SS) > 18 prior to first treatment
- Written informed consent.

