6.1 Baseline (before first treatment)

Patients for whom Cystistat is prescribed by the treating investigator will be enrolled in the study after signing a written informed consent form. No personal data will be recorded for the study before the consent procedure. Once eligible patients provide written informed consent, baseline assessments will be completed (this may be performed on the first treatment visit prior to instillation of Cystistat according to routine clinical practice):

- The investigator will review and document the patient's demography and medical history. This includes patients' demographic and anamnestic background data, diagnostic criteria of IC/BPS diagnosis, and previous and current treatments.
- Patients will be asked to complete the Bladder Pain/ Interstitial Cystitis Symptom Score (BPIC-SS). If the score is ≤ 18 , the patient will not be suitable for entering this NIS.
- The investigator will evaluate if the patient meets the inclusion/exclusion criteria.
- Patients will be asked to complete the Visual Analogue Scale (VAS) for bladder pain, urinary urgency, and quality of life (QoL).
- The investigator will assess and record any adverse events that occurred during this visit after signing the informed consent form.
- The investigator will provide the patient with the diary card and instruct her on how to record study related data at home. The following assessments are to be filled out by the patient:
 1. Morning voiding volume (once a week, preferably on the treatment day)
 2. Urinary voids and the respective volumes over a period of 24 hours (once a week, preferably starting the day before the treatment day)
 3. Use of concomitant IC/BPS medication, pain medication, and other relevant concomitant medication
 4. Adverse events
- A date for the next visit for the first treatment with Cystistat will be arranged and the investigator will remind the patient not to forget to take the diary card with her that day (not required if the first treatment with Cystistat is performed during the same visit according to routine clinical practice).
- The investigator will enter all required data from this visit in the eCRF within 5 business days.

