4.8 Schedule of Visits and Procedures

	Baseline ⁽¹⁾	During treatment	End of treatment ⁽²⁾	Follow-up ⁽³⁾
Study Day	Before first treatment	Week 1-11 (as per standard of care)	Latest week 12 (Month 3)	Approximately Month 6
Written informed consent	X			
Demography and medical history ⁽⁴⁾	X			
In-/exclusion criteria	X			
Patient Global Assessment of overall IC/BPS condition improvement ⁽⁵⁾			X	X
Assessment of BPIC-SS ⁽⁶⁾	X		X	X
Assessment of VAS ⁽⁷⁾	X		X	X
Instillation of Cystistat ⁽⁸⁾		X	X	(X)
Dispense of diary card ⁽⁹⁾	X		X	
Review of diary card		X	X	X
Collection of diary card			X	X
Assessment of concomitant medications ⁽¹⁰⁾		X	X	X
Assessment of adverse events, incidents ⁽¹¹⁾	X	X	X	X

- 1 Baseline assessments may be performed on the first treatment visit prior to instillation of Cystistat according to routine clinical practice.
- 2 This assessment will be performed on the last treatment day or latest at week 12; if required, treatment will be continued after week 12 under regular medical care.
- 3 Follow-up will be performed as an on-site visit if in accordance with routine clinical practice; if not possible as an on-site visit, the information will be collected remotely (e.g., via phone and postal mail) from the patient.
- 4 Demography and medical history:
 - Patients' demographic and anamnestic background data
 - Diagnostic criteria of IC/BPS diagnosis
 - Previous and current treatments
- 5 Patient Global Assessment of overall IC/BPS condition improvement: To be completed at end of treatment or latest at week 12 and at month 6.
- 6 Bladder Pain/ Interstitial Cystitis Symptom Score (BPIC-SS): To be completed prior to the first treatment, at end of treatment or latest at week 12, and at month 6.

Form Title: Statistical Analysis Plan

SOP Number: [REDACTED]	Current Version Number & Date: 1.0 & 30NOV2023	Previous Version Number & Document Date: 0.6 & 10NOV2023
---------------------------	---	--

- 7 Visual Analogue Scale (VAS) for bladder pain, urinary urgency, and quality of life (QoL): To be completed prior to first treatment, at end of treatment or latest at week 12, and at month 6.

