5.4 Baseline

Baseline value will be defined as the non-missing value before first treatment.

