5.5 Change from Baseline

Value of change from baseline at any post baseline visit will be defined as the difference of the non-missing baseline value to the non-missing post baseline value i.e.

Change from baseline (Δ) = post-baseline value at visit X - baseline value, where both values are non-missing.

Percent change from baseline will be calculated as:

$(\text{Assessment value at post-baseline visit X} - \text{baseline value}) / \text{baseline value} * 100$.

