7.2 Secondary Efficacy Variable Analysis

Secondary endpoints will be analyzed and reported as described below. Endpoint assessments will be tabulated by timepoint and in case of more than 2 timepoints additionally be displayed graphically as time course.

All changes from baseline will be analyzed by descriptive statistics for actual and change to end of treatment or latest week 12 and month 6 and reported using standard summary statistics. P-value will be calculated by using paired t-test for change from baseline. This is applicable for the following secondary endpoints:

- Morning voiding volume over time (from patient diaries, until month 6).

Form Title: Statistical Analysis Plan

SOP Number: [REDACTED]	Current Version Number & Date: 1.0 & 30NOV2023	Previous Version Number & Document Date: 0.6 & 10NOV2023
---------------------------	---	--

- Total number of voids and total voiding volume (daytime and nighttime) over the last 24 hours (from patient diaries, until month 6).

[figure not shown]
All changes from baseline will be analyzed by descriptive statistics for actual and change to end of treatment or latest week 12 and month 6 and reported using standard summary statistics. An ANCOVA model, as described below, will be used for baseline comparisons. This is applicable for the following secondary endpoints:

- Change from baseline to end of treatment or latest to week 12 and to month 6 in Bladder Pain/Interstitial Cystitis Symptom Score (BPIC-SS)
- Change from baseline to end of treatment or latest to week 12 and to month 6 in bladder pain and urinary urgency on Visual Analogue Scale (VAS) scored from 0 to 100.
- Change from baseline to end of treatment or latest to week 12 and to month 6 in quality of life (QoL) on Visual Analogue Scale (VAS) scored from 0 to 100.

The changes from baseline to end of treatment or latest week 12 and month 6 in above listed endpoints will be analyzed by Analysis of Covariance (ANCOVA). For the ANCOVA model, change from baseline will be the dependent variable and baseline will be the covariate. The analysis will be performed by using Proc Mixed. The covariance matrix will be left unstructured and the satterswaite approximation will be used for degrees of freedom.

Adjusted least square mean and the standard error values along with the p-value and the 95% confidence will be presented. Single effect for Week 12 and Month 6 will be derived as contrast from the overall model.

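### The one BPIC-SS reading that admits a patient is also her baseline, so regression to the mean alone moves this secondary endpoint and undermines a borderline p-value against zero

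*SAP*

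**What the plan says.** Protocol 4.2.1 requires "Bladder Pain/ Interstitial Cystitis Symptom Score (BPIC-SS) > 18 prior to first treatment". Protocol 6.1 has the patient complete the questionnaire at the baseline visit; with a score of 18 or less, "the patient will not be suitable for entering this NIS". The schedule in SAP 4.8 plans one BPIC-SS before treatment: "To be completed prior to the first treatment, at end of treatment or latest at week 12, and at month 6".

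That reading then becomes the baseline. SAP 5.4: "Baseline value will be defined as the non-missing value before first treatment". SAP 5.5 defines change as "post-baseline value at visit X - baseline value, where both values are non-missing". SAP 5.3 confirms that there is only one treatment group.

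For BPIC-SS and the VAS scales, SAP 7.2 specifies: "For the ANCOVA model, change from baseline will be the dependent variable and baseline will be the covariate". On output it says: "Adjusted least square mean and the standard error values along with the p-value and the 95% confidence will be presented", and on visits: "Single effect for Week 12 and Month 6 will be derived as contrast from the overall model". Protocol 8.3 and SAP 5.10 call the analyses exploratory. Neither document mentions regression to the mean, a second pre-treatment reading, or caution in reading this p-value.

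**The concern.** A patient whose score is high by chance on the entry day passes the cut; one whose score is low by chance is turned away. On re-measurement the admitted group drifts back towards its usual level, so the expected change is negative even if the device does nothing. More patients do not cure this: a fixed bias with a shrinking standard error is declared significant more often.

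What is at stake is the reading of one p-value. BPIC-SS is the instrument that Protocol 7.1.2 calls validated, and SAP 1.0 foresees the planned analyses going into regulatory submissions, if applicable, and manuscripts. A modest but significant fall could be taken as evidence of performance when selection could have produced it.

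**Working it through.** **Sample size.** Protocol 8.1 and SAP 5.1 give 74 patients, including 7 for dropout: 74 - 7 = 67, and 67 x 1.10 = 73.7, rounded to 74. The stated total reproduces. The basis for the 67 is redacted. I use n = 67.

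**Inputs.** From the documents: entry above 18 on an integer score from 0 to 38; one group; 95% interval. Assumed, because the documents give none: unselected mean (mu) 20-28, SD 6-7, test-retest reliability (r) 0.60-0.85, no treatment effect.

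**Expected fall.** With z = (18.5 - mu)/SD and lambda = phi(z)/(1 - Phi(z)), the fall is (1 - r) x SD x lambda. For mu = 23, SD = 6, r = 0.75:
- z = -4.5/6 = -0.75; lambda = 0.301/0.773 = 0.389; SD x lambda = 2.34.
- Fall = 0.25 x 2.34 = 0.58 points.
- Baseline variance after selection = 36 x (1 + z lambda - lambda^2) = 20.0. Variance of change = 0.25^2 x 20.0 + 36 x (1 - 0.75^2) = 17.0, so SD 4.12.
- Noncentrality = 0.58/4.12 x sqrt(67) = 1.16, so a two-sided 5% t-test rejects in 21% of null studies.

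| mu / SD / r | SD x lambda | Fall (points) | Rejection, t-test |
|---|---|---|---|
| 20 / 7 / 0.60 | 4.67 | 1.87 | 73% |
| 23 / 7 / 0.75 | 3.07 | 0.77 | 25% |
| 23 / 6 / 0.75 | 2.34 | 0.58 | 21% |
| 26 / 6 / 0.85 | 1.22 | 0.18 | 7% |
| 28 / 6 / 0.85 | 0.72 | 0.11 | 6% |

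Simulating the ANCOVA itself gives slightly higher rejection, because its residual variance is smaller: about 75% in the first row, 23-28% at mu = 23, and about 7-8% at mu = 26-28.

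**Why the covariate does not help.** With no effect, the expected change at baseline x is -(1 - r)(x - mu). The LS mean is taken at the selected-sample mean, mu + SD x lambda, and so returns the full fall. In one group it equals the raw mean change (complete data).

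**What isolates the cause.** In a simulation with SD 6 and r 0.6-0.9, taking a separate pre-treatment reading as baseline brought the mean change to about 0 (-0.02 to +0.02). False significant improvement was about 2-5%, against 4-73% as planned (nominal 2.5% in that direction).

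**What the existing data can do.** The expression above is zero at x = mu. Reading the fitted line at the unselected mean therefore removes the shift, and the fitted slope supplies r. In simulation this gave bias near 0 and 4-6% rejection when mu was right. For 23/6/0.75 the residual SD is sqrt(15.75) = 3.97. The 95% half-width grows from 1.997 x 3.97 x sqrt(1/67) = 0.97 to 1.997 x 3.97 x sqrt(1/67 + 2.34^2/(66 x 20.0)) = 1.09. An assumed mu that is wrong by 2 points moves the estimate by 2 x 0.25 = 0.5 points.

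**The case against.** - **Weight.** BPIC-SS is one of several secondary endpoints, everything is labelled exploratory, and no success rule is tied to this p-value. The null of zero is inferred; the SAP does not write it. This stands, and it limits the point to interpretation. A reader might infer that the study's main conclusion is compromised, but the primary endpoint is a PGA responder rate that uses no BPIC-SS baseline.
- **Size.** It rests wholly on assumed inputs. The 20/7/0.60 corner implies that about 41% of otherwise suitable patients fail the cut, and nothing in the documents suggests that: patients already have a diagnosis, at least 6 months of pain and a prescription. At mu = 23 the fall of 0.6-0.8 points lies inside the expected 95% half-width of 1.0-1.2. This also stands. A reader might infer that any BPIC-SS improvement would be an artefact; the figures do not support that.
- **Other biases.** Natural course and placebo response also shift a one-arm mean, and Protocol 3.2 reports an initial placebo response above that of Cystistat. Correcting regression to the mean alone does not isolate a device effect. This is true, so the fix must say so.
- **VAS.** One might infer that the VAS scales are free of the problem because they do not decide entry. They are completed at the same visit. If day-to-day fluctuation correlates 0.5 with BPIC-SS (assumed), VAS tests against zero reject in about 9-13% of null studies at mu = 23 and 15-22% at mu = 20. They are less affected, not unaffected.

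The exploratory label does not answer the point itself: it does not give the p-value a valid reference.

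**Conclusion.** The concern holds in a limited form. One reading serves as entry test and baseline, and the one-arm ANCOVA is in effect tested against zero. Regression to the mean alone shifts the BPIC-SS change by roughly 0.1-1.9 points and raises two-sided rejection from 5% to about 7-75%, for an unselected mean of 20-28, SD 6-7, reliability 0.60-0.85 and n = 67. At the mild end (unselected mean 26-28 with high reliability) the effect is close to negligible; it matters when many candidates score near the cut. It threatens a borderline p-value and the reading of a modest change. It cannot account for a large fall on a 0-38 scale, and it does not touch the primary analysis. A change worth making, not a fatal flaw.

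**What to change.** In SAP 7.2:

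1. Keep the planned BPIC-SS LS mean and 95% CI. Beside them add a sensitivity row with the same ANCOVA estimate and CI evaluated at assumed unselected baseline means of 20, 22, 24, 26 and 28, using a baseline slope for each visit. All five values lie above the entry cut, and no reliability has to be assumed. If BPIC-SS scores of consented patients who failed the cut were captured, use them to inform the mean. State that the row assumes an effect that does not vary with baseline.
2. Do not present the BPIC-SS p-value against zero as evidence of performance. Report the estimate and CI, and state that regression to the mean, natural course and placebo response are not separated from the device effect.
3. Describe the VAS scales as not directly selected on and less affected.

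A separate baseline reading would be cleaner, but the protocol planned the study to end in Q3 2023 and the SAP is dated 30 November 2023, so it is probably too late. Fitting a truncated normal to the admitted baselines is too unstable: in simulation the 95% range for SD x lambda was 0.6-6.8 against a true 2.3.

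Cost: one paragraph and a few table entries, with no new data. The unselected mean must be assumed over a range, the intervals in the added row are somewhat wider, and the BPIC-SS statement becomes less favourable.

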7.1.7 Occurrence of Flares

Flares are defined as symptom deteriorations and will be considered as adverse events. Adverse events will be recorded by the patient in the diary and also assessed and recorded by the investigator at the weekly controls/instillations and at the follow-up visit. In case of a flare, and additional BPIC-SS (see [Section 7.1.2](#)) will be completed by the patient at the time of occurrence.

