- 8 Instillation of Cystistat: Cystistat will be instilled into the bladder according to the instructions for use; the regimen and duration of treatment will depend on the investigators' discretion; each instillation of Cystistat until month 6 will be recorded in the eCRF; the observation period for this study will end approximately at month 6 (irrespective of the duration of treatment); if required, treatment will be continued after month 6 under regular medical care.
- 9 Diary card: The following assessments are to be filled out by the patient:
 - Morning voiding volume once a week, preferably on the treatment day (until end of treatment or latest week 12) and once at month 6
 - Urinary voids and the respective volumes over a period of 24 hours once a week, preferably starting the day before the treatment day (until end of treatment or latest week 12) and once at month 6
 - Use of concomitant IC/BPS medication, pain medication, and other relevant concomitant medication (until month 6)
 - Adverse events (until month 6)
- 10 The use of concomitant IC/BPS medication, pain medication, and other relevant concomitant medication will be recorded; it is not required to collect all concomitant medication.
- 11 Adverse events and incidents will be recorded after the first instillation of Cystistat; prior to first instillation of Cystistat only adverse events will be recorded.

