The Proc mixed procedure of SAS will be used to compare the change from baseline for Bladder Pain/Interstitial Cystitis Symptom Score (BPIC-SS) by adjustment of continuous baseline values.

The following secondary endpoints will be analyzed and reported like the analysis method and reporting of the primary endpoint as described above:

- Percent responders at month 6 as indicated by change on the 7-point Patient Global Assessment (PGA) scale using the same responder definition as for the primary endpoint.

Form Title: Statistical Analysis Plan

SOP Number: [REDACTED]	Current Version Number & Date: 1.0 & 30NOV2023	Previous Version Number & Document Date: 0.6 & 10NOV2023
---------------------------	---	--

- Percent responders at the end of treatment or latest at week 12 and at month 6 as indicated by change on the 7-point Patient Global Assessment (PGA) scale using an alternative responder definition (i.e. a responder is defined as a patient who experiences moderate or marked improvement).

The following secondary endpoints will be presented by summary statistics:

- Counts and percentages will be presented for occurrence of flares (documented as adverse events) and descriptive statistics will be presented for additional BPIC-SS (at the time of occurrence) (until month 6) by summary statistics.
- Number and percentage of premature termination of treatment will be presented by using frequency tables.
- Use of concomitant IC/BPS and pain medication count (until month 6) will be presented by using frequency tables.

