7.3 Subgroup Analysis

A subgroup of patients who have at least 4 treatments in first 25 days of treatment will be analyzed separately to reflect treatment recommendation, if relevantly different from the Full Analysis Set (FAS) (less than 80% of Full Analysis Set (FAS)). Descriptive statistics will be done for all primary and secondary efficacy analyses by using subgroup analysis population.

If there is a substantial rate of patients with early termination before end of treatment or latest week 12 (n>10), a separate subgroup for patients with available data for end of treatment visit or latest week 12 analyses will be performed.

Additional subgroups regarding concomitant IC/BPS, pain medication, specific treatments schedule or deviation of in-/exclusion criteria might be meaningful and will be analysed exploratively.

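### Flares are reported as one count and percentage to month 6, although review intensity changes when instillations stop and early leavers stay in the denominator

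*SAP*

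**What the plan says.** - **Capture.** Protocol section 7.1.7 treats flares as adverse events. "Adverse events will be recorded by the patient in the diary", and they are "also assessed and recorded by the investigator at the weekly controls/instillations and at the follow-up visit". SAP section 4.8, note 9, lists among the diary items "Adverse events (until month 6"), so the diary runs on after treatment stops. A diary card is handed out at the end-of-treatment visit for this purpose (Protocol section 6.3).
- **Length of treatment.** SAP section 4.8, note 8: "the regimen and duration of treatment will depend on the investigators' discretion". Observation lasts about 6 months whatever the treatment duration (SAP section 4.2). Instillations after week 12 are possible (SAP section 5.8).
- **Analysis.** SAP section 7.2: "Counts and percentages will be presented for occurrence of flares (documented as adverse events"), until month 6. A general sentence in that section promises tabulation by timepoint, but the flare item names no timepoints, so a single pooled result is the natural reading.
- **Denominator.** SAP section 5.0 bases percentages on all patients in the population unless stated otherwise. Withdrawn patients contribute data up to withdrawal, and nothing is imputed (SAP section 5.11). About 10% are expected to drop out before the end-of-treatment or week-12 visit (SAP section 5.1).
- **Subgroups.** SAP section 7.3 defines a subgroup with at least 4 treatments in the first 25 days, produced only if it is below 80% of the FAS. For it, "Descriptive statistics will be done for all primary and secondary efficacy analyses by using subgroup analysis population", which includes flares. Further subgroups by "specific treatments schedule or deviation of in-/exclusion criteria might be meaningful and will be analysed exploratively".

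**The concern.** The single percentage mixes two kinds of follow-up. During instillations someone reads the diary and asks about events roughly every week. After the last instillation the next scheduled reading may be months later, possibly by phone and post. The point at which one gives way to the other is set by each patient's own course of treatment. If the diary alone misses some flares, the pooled figure understates them, and patients with different courses are measured with different sensitivity.

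The second problem needs no assumption about diary quality. A percentage labelled until month 6 implies that every patient in the denominator was watched to month 6. Early leavers were not.

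What is at stake is the reading of one named secondary endpoint, and of any flare table for a subgroup defined by treatment schedule. The primary endpoint is not affected.

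**Working it through.** **The plan's own figure.** The documents give no flare rate, so the only figure to reproduce is the dropout allowance. The implied base is 74 − 7 = 67. Ten per cent of 67 is 6.7, rounded to 7, and 67 + 7 = 74. (Dividing instead, 67/0.9 = 74.4, rounds up to 75.) The base of 67 cannot be checked because its derivation is redacted. The 10% is used below.

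**Early leavers.** Assume a constant true rate of λ flares per 26 weeks, full capture while observed, departure unrelated to flares, and 10% of patients leaving at week 4. The 10% is the plan's figure; λ and week 4 are assumptions.

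- Fully observed: 1 − exp(−λ).
- As reported: 0.9 × [1 − exp(−λ)] + 0.1 × [1 − exp(−4λ/26)].
- For λ = 1: fully observed 63.2%; as reported 0.9 × 63.2% + 0.1 × 14.3% = 58.3%.

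| λ (assumed) | Fully observed | As reported | Shortfall (points) |
|---|---|---|---|
| 0.25 | 22.1% | 20.3% | 1.8 |
| 0.5 | 39.3% | 36.2% | 3.2 |
| 1 | 63.2% | 58.3% | 4.9 |
| 2 | 86.5% | 80.5% | 6.0 |

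If the 10% leave at week 12 instead, λ = 1 gives 0.9 × 63.2% + 0.1 × 37.0% = 60.6%.

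A rate removes this dilution under the same assumptions. Expected flares per patient are 0.9 × 1 + 0.1 × 4/26 = 0.915. Weeks observed per patient are 0.9 × 26 + 0.1 × 4 = 23.8. The ratio is 0.0385 per week, which is the true 1/26.

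**Review intensity.** For a patient treated T of 26 weeks with no later visits, the scheduled gap before the month-6 review is 26 − T: 14 weeks for T = 12 and 22 weeks for T = 4 (both course lengths are assumed). Let capture be 1 under weekly review and d afterwards. Recorded flares are then proportional to T + d(26 − T). The table gives the ratio of a 12-week to a 4-week patient. The first ratio assumes the same true flare rate on and off treatment, and the second a rate on treatment that is half the rate off it.

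| d (assumed) | Equal rates: (12 + 14d)/(4 + 22d) | Half on treatment: (6 + 14d)/(2 + 22d) |
|---|---|---|
| 1.0 | 1.00 | 0.83 |
| 0.7 | 1.12 | 0.91 |
| 0.5 | 1.27 | 1.00 |
| 0.3 | 1.53 | 1.19 |

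With equal rates and d = 0.9 the ratio is 1.03. Unequal review alone thus adds between nothing and 53% over this range. The observed ratio can fall on either side of 1, depending on true rates that the documents do not give.

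**The case against.** The strongest reply is that capture does not stop when instillations stop. Patients record adverse events in the diary to month 6, that diary is reviewed and collected at follow-up, and Protocol section 10.2 requires the investigator to ask about events at every contact. Patients treated beyond week 12 have further visits. No figure in the documents suggests that the diary misses flares. All of this stands. It makes unequal capture a risk of unknown size, possibly zero.

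A reader might infer that longer-treated patients must show more flares by construction. The documents do not support that: there is no excess at equal capture, and the sign also depends on the true rates on and off treatment. A reader might also infer that the SAP plans to compare flares by treatment duration. It does not. The one named schedule subgroup is conditional, descriptive and defined by early intensity; any others are optional and undefined. With an FAS of about 67, it would be produced only at 53 patients or fewer (0.8 × 67 = 53.6).

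The consequence is also modest. The study is single-arm and exploratory, and patient listings are planned. If 67 patients were split equally, the standard error of a difference between percentages near 50% would be √(0.25 × 2/33.5), about 12 points. That exceeds the 4.2-point gap (56.8% against 52.6%) between 12-week and 4-week patients at d = 0.7 and 1 flare per 26 weeks.

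None of this answers the denominator point. Protocol section 6.5 asks for diary and event data at withdrawal, which secures the time before leaving but not the time after.

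**Conclusion.** The point holds as a reporting weakness with a cheap remedy. Two parts rest on the documents alone: the pooled result to month 6 has no period split and no patient-time, and early leavers without a recorded flare count as flare-free for unobserved time. The latter biases the percentage low. The illustration is about 58% instead of 63%, and the shortfall runs from 1.8 to 6.0 points over 0.25 to 2 flares per 26 weeks. It rests on the assumed flare rate, on departure at week 4, and on departure being unrelated to flares.

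The third part, different capture on and off treatment, is a possibility whose size is unknown and may be nil. It gives no assured direction for a comparison between patients with longer and shorter courses. It does justify showing the two periods separately, and caution over any flare difference between a schedule subgroup and the FAS. The 4-in-25-days criterion also selects patients with more review visits in those days.

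**What to change.** In SAP section 7.2, tabulate flares by onset date in two periods: first instillation to the end-of-treatment or week-12 visit, and that visit to month 6. For each, give patients at risk, patient-weeks observed, number of flares and flares per patient-week. Add a note that the later period rests mainly on the diary and recall unless treatment visits continued.

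In SAP section 7.3, state that flare differences between the 4-in-25-days subgroup, or any other schedule subgroup, and the FAS may reflect the number of review visits. Show review visits per patient alongside.

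Restricting subgroup comparisons to the first 4 weeks would not solve the problem, because the subgroup definition itself separates patients by how often they attended in that window.

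The cost is SAP wording and one table. Event onset dates (Protocol section 10.2) and instillations (SAP section 4.8, note 8) are already recorded, and visit and withdrawal dates supply the patient-time. The downside is fewer events in each period.
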